Title: Applying videos feedback Learning to Improve Skills Performance of Physiotherapy Interns

[name], PT, MS,
Department of Physical Medicine and Rehabilitation, Wang Fang Hospital,
Taipei
Medical University, Taipei, Taiwan
[contact] [name]
Email: [contact]

Background

This project uses self-practicing videos feedback to learn to improve the skill performance of physiotherapy interns. For traditional physiotherapy intern courses, teachers will conduct core courses and demonstrate teaching, but students are less familiar with the application of skills, even if adding practice course. The learning outcomes of the course are still not good in skill performance. By recording the self-practicing videos, the teacher uses observation and feedback to let the physiotherapy interns know whether the posture of the individual case, the fixed position of the limbs are appropriate, the resistance given and whether the verbal instruction is correct, and based on the evaluation outcomes to observe the students' learning status and clinical thinking ability can improve the skill performance and learning satisfaction.

Methods

This study is divided into three randomized controlled experiments, recruiting physical therapy interns. During the internship period, participants will execute various station-based internships according to the instructional plan. Prior to the trial, the project lead will explain the research plan to students, and willing participants will sign an informed consent form before participating in the study. Interns who are not willing to participate will still be involved in course design but will not undergo assessment tests.

1. Participants

Inclusion criteria for physical therapy interns require individuals to be over 20 years old. Exclusion criteria include individuals unwilling to participate in the study.

The study uses sealed envelopes for random allocation to ensure evaluator blinding. Evaluators are unaware of which group each participant is assigned to, with an internal reliability of 0.93. Participants are divided into two groups: practice group and video feedback group, each consisting of 45 individuals.

2. Interventions

2.1 Practice Group: Participants in this group engage in the traditional core course (1-hour lecture on upper limb soft tissue differential diagnosis and assessment techniques. They have the opportunity to observe teacher demonstrations, and the course content and instructional

demonstrations are consistent and delivered by the same therapist), followed by a 20-minute practical session where they pair up for mutual hands-on practice. The assessment of upper limb soft tissue operations takes approximately 4 minutes per session, allowing for approximately 5 practice sessions.

2.2 Video Feedback Group: Participants receive the traditional core course along with a 20-minute video feedback session. Initially, a therapist records students' assessment techniques in action, capturing the dynamic process on video. The recorded video is then played on a screen for both the course teacher and students to watch together. Participants can annotate specific actions during the viewing, and the course teacher facilitates a reflective discussion where participants observe and identify any issues or correct actions as expected. The teacher provides feedback on areas of improvement in the action process for further practice. The self-viewing of the recorded video serves as a valuable tool for enhancing the skill performance of physical therapy interns

3. Outcome Measures

3.1 Objective Structured Clinical Examination (OSCE): Evaluators utilize a detailed, operationally defined standardized checklist to assess the performance of examinees in a structured clinical skills assessment. OSCE is a performance-based testing method that objectively evaluates clinical skills in simulated clinical scenarios using molds and standardized patients. This instructional design aims to aid students in learning and understanding their learning outcomes, evaluating the knowledge, skills, and attitudes of the examinees through a performance-based testing approach.

The scoring sheet includes an standardized checklist and an overall performance assessment. The standardized checklist comprises 15 items, with results presented in percentages, where higher scores indicate better performance. The overall performance assessment ranges from 5 points (excellent) to 1 point (poor).

Time Frame: pre-test, within 1 week post test, 3-month follow-up.

3.2 Mini-Clinical Evaluation Exercise (Mini-CEX): The Mini-CEX focuses on the performance of interactions with patients. Clinical instructors can use it to directly observe the interaction between learners and patients, conduct a simple assessment of the Mini-CEX, and provide direct

feedback to the learners. Clinical instructors can assess a specific aspect (medical interview, physical examination, operational skills, counseling and health education, clinical judgment, organizational efficiency, humanitarian professionalism) each time.

The assessment consists of 7 items, with scores ranging from 1 to 9 points each. The total score ranges from 7 to 63 points, with higher scores indicating better performance.

Time Frame: pre-test, within 1 week post test, 3-month follow-up.

3.3 Direct Observation of Procedural Skills (DOPS): Clinical instructors assess and provide feedback on the procedural skills of participants, ensuring effective learning. Clinical instructors evaluate and provide feedback on the procedural skills of the examinee. Each clinical procedural skill is assessed and feedback is provided to ensure learning effectiveness.

The assessment consists of 10 items, with scores ranging from 1 to 6 points each. The total score ranges from 10 to 60 points, with higher scores indicating better performance.

3.4 Course Satisfaction: Understand your satisfaction with various arrangements of this course activity, including speakers, lecture content, and related activities.

The assessment consists of 12 items, with scores ranging from 1 to 5 points each. The total score ranges from 12 to 60 points, with higher scores indicating higher satisfaction.

4. Statistical analysis

All analyses were conducted via the IBM SPSS statistical software, version 23.0. The continuous data were presented in means and standard deviations, and number and percentage for categorical data. Independent t-test was used to compare continuous data and chi-square for categorical data. Inferential statistics were performed using a generalized estimating equations to estimate the intervention effectiveness of the simulation course. The significance level was set to 0.05. Intention-to-treat (ITT) analysis is an approach to managing dropouts and missing data. Sample size was calculated using G*Power to compare differences between variables and independent means. A power of 80% was used, with medium effect size (Cohen's d) of 0.5, and alpha significance level of 5%. This resulted in a sample size of 54 students (Rotthoff, 2014).

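### For OSCE and Mini-CEX, Section 4 does not state the GEE's outcome times, contrast or use of the pre-test; adjusting for the scheduled pre-test would add precision at almost no cost

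*Combined protocol and SAP*

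**What the plan says.** The main inference is one sentence in Section 4 (Statistical analysis): "Inferential statistics were performed using a generalized estimating equations to estimate the intervention effectiveness of the simulation course". The same section names an independent t-test for continuous data, with no time point and no stated relation to the GEE. On missing data it says only: "Intention-to-treat (ITT) analysis is an approach to managing dropouts and missing data".

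Sections 3.1 (OSCE) and 3.2 (Mini-CEX) each print the same schedule: "Time Frame: pre-test, within 1 week post test, 3-month follow-up". OSCE yields two scores, a 15-item checklist percentage and a 1-5 overall rating. Mini-CEX yields a 7-item total, although Section 3.2 also says "Clinical instructors can assess a specific aspect" on each occasion. Sections 3.3 (DOPS) and 3.4 (course satisfaction) print no time frame.

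On size, Section 1 (Participants) says "Participants are divided into two groups: practice group and video feedback group, each consisting of 45 individuals", while Section 4 says "This resulted in a sample size of 54 students". Methods adds: "This study is divided into three randomized controlled experiments". How 45 per group relates to those three experiments is not stated.

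**The concern.** With three scheduled scores and one sentence on the model, several analyses fit the text: a comparison of post scores that ignores the pre-test, a group-by-time (change) contrast, or a comparison of post scores adjusted for the pre-test. They differ in precision, and the third uses a score the trial already plans to collect.

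Two things are at stake. The first is precision, in a trial that does not reach its own 80% target at d = 0.5 under a two-sided independent-means comparison, either with 54 students or with 45 per group. The second is pre-specification: as written, the choice between valid contrasts, post times and scores can be made after the data are seen.

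**Working it through.** **Inputs from the documents.** d = 0.5, alpha 5%, power 80%, 54 students (Section 4); 45 per group (Section 1).

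**Assumptions.** Two-sided test; r = 0.3, 0.5, 0.7; post-test SD 1; pre-test SD equal to it unless stated; continuous score; one post time; no dropout; 45 per group as the analysed size.

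**The plan's own figure.** Two independent means with d = 0.5, two-sided 5% and 80% power need 64 per group, 128 in total (one-sided: 51 per group, 102). The stated 54 is not reproduced. That is a separate issue and nothing below depends on it. Power for d = 0.5 is 44% at 27 per group and 65% at 45 per group.

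**Step 1: variance factors at one post time.** Unadjusted: 1. Change contrast: 2(1 - r). Pre-test as covariate: 1 - r^2. The ratios to the adjusted factor are 1/(1 - r^2) for the unadjusted comparison and 2/(1 + r) for the change contrast.

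**Step 2: power at 45 per group.** The noncentrality is 0.5 x sqrt(45/2) / sqrt(factor) = 2.372 / sqrt(factor), with 88 df, or 87 with the covariate.

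| r | Unadjusted | Change | Adjusted |
|---|---|---|---|
| 0.3 | 2.372, 65% | 2.372/sqrt(1.40) = 2.00, 51% | 2.372/sqrt(0.91) = 2.49, 69% |
| 0.5 | 2.372, 65% | 2.372/sqrt(1.00) = 2.37, 65% | 2.372/sqrt(0.75) = 2.74, 77% |
| 0.7 | 2.372, 65% | 2.372/sqrt(0.60) = 3.06, 86% | 2.372/sqrt(0.51) = 3.32, 91% |

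In participants, 45 per group adjusted matches 45/(1 - r^2) = 49.5, 60.0, 88.2 per group unadjusted, or 45 x 2/(1 + r) = 69.2, 60.0, 52.9 per group with the change contrast. At 27 per group, power is 44% unadjusted; 33%, 44%, 64% for change; and 47%, 55%, 71% adjusted.

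**Step 3: unequal SDs.** Let k be the pre-test SD divided by the post-test SD. The change factor becomes 1 + k^2 - 2rk; the adjusted factor stays 1 - r^2. At r = 0.5:
- k = 0.5: 1 + 0.25 - 0.5 = 0.75, equal to the adjusted 0.75, so no gain.
- k = 1.5: 1 + 2.25 - 1.5 = 1.75, a ratio of 1.75/0.75 = 2.33.

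**Step 4: missing pre-tests.** Suppose 10% are missing completely at random.
- If those participants are dropped, n is 40.5 per group. At r = 0.3 the noncentrality is 0.5 x sqrt(20.25)/sqrt(0.91) = 2.36, about 64%. Simulation with robust standard errors gives 63%. Both are below the unadjusted 65%.
- If the overall pre-test mean is filled in, the covariate has variance 0.9 and covariance 0.9r with the outcome. The factor is 1 - (0.9r)^2/0.9 = 1 - 0.9r^2. At r = 0.3 this is 0.919, the noncentrality is 2.372/sqrt(0.919) = 2.47, and power is about 69%.

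**Step 5: a three-time model with equal baseline means.** A GEE with one common scale uses phi = (k^2 + 2)/3 and gives the pre-test the weight b = rk/phi, where the best weight is r/k. The resulting factor is 1 - 2brk + b^2k^2.
- k = 1: b = r and the factor is 1 - r^2, the full gain.
- k = 1.5, r = 0.7: phi = 1.417, b = 0.741, factor = 1 - 1.556 + 1.236 = 0.680. Power is about 81%, against 91% for the covariate model.
- k = 2: phi = 2, b = r, factor = 1 - 4r^2 + 4r^2 = 1, so no gain at any r.
- With an independent working correlation there is no adjustment; simulated power is 64% at every r.

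**Step 6: one post time or the average of both.** With equal correlations among the three scores, the adjusted factor for the average is (1 + r)/2 - r^2, which is 0.50 at r = 0.5. The average beats 1 week alone when its mean effect exceeds 0.5 x sqrt(0.50/0.75) = 0.408, that is, when the 3-month effect exceeds 2 x 0.408 - 0.5 = 0.32. If that effect falls to 0.25, power for the average is 65%, 70%, 83% at the three values of r, below the adjusted 1-week figures in Step 2.

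**The case against.** The strongest reply is that no error has been shown. The text does not exclude adjustment, the unadjusted and change contrasts are both valid, and the protocol is very short. The gain also depends on quantities the documents do not give. Against the unadjusted comparison it is 4 points at r = 0.3 (65% to 69%); against the change contrast it is 5 points at r = 0.7 (86% to 91%), and Step 3 shows it can be nil. A covariate model that drops participants without a pre-test can do worse than no adjustment and sits badly with the ITT statement.

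All of this stands. It limits the size of the point and shapes the fix. It does not remove the point: with complete pre-tests the adjusted variance is never larger than either alternative, apart from one degree of freedom, and the missing specification remains.

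A reader might infer more: that the plan forgoes baseline adjustment, or that its analysis will be biased. The documents do not support either reading, because they are silent on the matter. A reader might also suppose that the effect will be a group main effect averaged over all three times. That would shrink a constant post-intervention effect of 0.5 to 2/3 of its size, 0.33, but nothing in Section 4 says this contrast is intended.

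**Conclusion.** The point holds as a precision improvement and a request to state the model; it is not a finding of error. For OSCE and Mini-CEX, Section 4 leaves open the outcome times, the contrast and the role of the pre-test, and no other section supplies them. Under the assumptions listed, at 45 per group and r = 0.5, pre-test adjustment raises power from 65% under either alternative to 77%.

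The size rests on an assumed r, on equal pre- and post-test SDs for the change-contrast comparison, on complete pre-tests, and on 45 per group being the analysed size. The missing-data figures assume pre-tests missing completely at random; they say nothing about other mechanisms. The power figures are for a continuous score and have not been shown to apply to the 1-5 OSCE rating. DOPS and course satisfaction are outside the point, since no time frame is printed for them.

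**What to change.** In Section 4, for the OSCE checklist percentage, the OSCE 1-5 rating (as a mean difference) and the Mini-CEX total (only if all 7 items are scored at each time):

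- Fit the GEE to the within-1-week and 3-month scores with pre-test score, group, time and group x time as terms, and robust standard errors.
- Fill in a missing pre-test by a simple rule that ignores group, such as the overall pre-test mean, so that every randomised participant with a post score is analysed.
- Name in advance the primary score and the primary time (or the average of both). Report the adjusted group difference with its 95% CI.
- Limit the independent t-test of these scores to descriptive or baseline comparisons, so that it is not a second route to the treatment effect.
- Use a three-time model with equal baseline means only if its variance may differ by time and its correlation is not set to independence.

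The cost is a few sentences of analysis wording and one degree of freedom. The scores are already scheduled, and the method and software are already named.

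### Five scores share one 0.05 level with no primary score, GEE contrast or time point named, so the plan does not say which result answers the question

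*Combined protocol and SAP*

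**What the plan says.** **Scores.** Section 3.1 gives two OSCE results: "The scoring sheet includes an standardized checklist and an overall performance assessment". The first is a percentage over 15 items and the second a 1-5 rating. Sections 3.2 to 3.4 add Mini-CEX (7-63), DOPS (10-60) and course satisfaction (12-60). That makes five scores, and none is called primary or secondary.

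**Times.** Sections 3.1 and 3.2 both carry the line "Time Frame: pre-test, within 1 week post test, 3-month follow-up", and neither post-course time is singled out. Sections 3.3 and 3.4 give no assessment time.

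**Analysis.** Section 4 says "Independent t-test was used to compare continuous data and chi-square for categorical data", without saying whether this is for baseline or outcome data. It then says "Inferential statistics were performed using a generalized estimating equations to estimate the intervention effectiveness of the simulation course", without naming an outcome, model term or time. One level applies throughout: "The significance level was set to 0.05". There is no testing order and no multiplicity adjustment.

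**Aim.** The Background expects that the method "can improve the skill performance and learning satisfaction", so it singles out neither one skill score nor skill alone.

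**Design and size.** Methods opens with "This study is divided into three randomized controlled experiments, recruiting physical therapy interns". Section 1 describes two groups, "each consisting of 45 individuals". The sample-size text in section 4 names independent means, d = 0.5, 80% power and 5% alpha, arrives at 54 students, and names no outcome.

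**The concern.** A 5% level describes the error rate of one decision. Here five scores, and at least two possible times for three of them, can each be tested at 5%, and nothing written down says which test decides. If the authors or readers treat any significant score as showing that video feedback works, the stated level is not the error rate of that conclusion.

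There is also a problem of interpretation that does not depend on error rates. The one-week and three-month results may disagree, or the OSCE checklist may disagree with DOPS. The plan gives no basis for saying which result answers the question. The sample-size text cannot supply an implied primary outcome, because it names none.

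**Working it through.** **1. The plan's own figure: 54 students.**
Inputs from section 4: d = 0.5, power 80%, alpha 5%, independent means. Sidedness is not stated, so both are tried.

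- Normal approximation, n per group = 2(z_alpha + z_power)²/d².
  - Two-sided: 2(1.960 + 0.842)²/0.25 = 62.8, so 63.
  - One-sided: 2(1.645 + 0.842)²/0.25 = 49.5, so 50.
- Noncentral t, the exact calculation: 63.8, so 64 per group two-sided (128 in total); 50.2, so 51 per group one-sided (102 in total).
- If 54 is the total (27 per group), power is 44% two-sided or 57% one-sided. If it is per group, power is 73% or 83%.

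The stated inputs do not lead to 54 on any of these readings.

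**2. Number of tests.**
One test per score gives 5. One test per stated post-course time gives OSCE checklist 2 + OSCE rating 2 + Mini-CEX 2 + DOPS 1 + satisfaction 1 = 8, where the single time for the last two is an assumption.

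**3. Chance of at least one false positive.**
Assumptions: no true effect on any score, each test two-sided at 0.05, one pooled comparison, and a common correlation ρ between the five test statistics. The documents give no ρ, so a range is shown. With c = 1.96:

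P = 1 − ∫ φ(u) [Φ((c − √ρ u)/√(1−ρ)) − Φ((−c − √ρ u)/√(1−ρ))]⁵ du

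At ρ = 0 this is 1 − 0.95⁵ = 0.226. To count only errors favouring video feedback, drop the second Φ term.

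| ρ | Either direction | Favouring video feedback |
|---|---|---|
| 0 | 22.6% | 11.9% |
| 0.5 | 18.3% | 9.2% |
| 0.8 | 12.7% | 6.4% |
| 0.9 | 10.2% | 5.1% |
| One test only | 5% | 2.5% |

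Sensitivity to the count, either direction, ρ = 0.8 to 0.5:
- three scores (one each from OSCE, Mini-CEX and DOPS): 10-13%
- four scores (satisfaction left out, or one score per instrument): 11-16%
- eight tests, with an assumed between-time correlation of 0.6 (by simulation): 19-26%, of which about 10-13% favours video feedback

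**4. Power at the planned 45 per group.**
Two-sided 5%, d = 0.5 on the post-test SD scale, equal SDs before and after. A post-test comparison has 65% power. For change from pre-test the effective d is 0.5/√(2(1−r)); with baseline adjustment it is 0.5/√(1−r²), where r is the pre-post correlation. At r = 0.6, for example, these are 0.5/√0.8 = 0.559 and 0.5/√0.64 = 0.625.

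| r | Change | Baseline-adjusted |
|---|---|---|
| 0.3 | 51% | 69% |
| 0.5 | 65% | 77% |
| 0.6 | 75% | 83% |
| 0.7 | 86% | 91% |

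The documents give no r.

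**The case against.** The strongest reply is that this is an educational trial whose plan makes no confirmatory claim and nowhere says that one significant score is enough. That is true, and it is why the percentages are conditional. It does not remove the gap: the plan is randomized, sets a significance level and calculates power, so it is set up as a test, yet it does not say of what.

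Five stronger readings are tempting, and the documents do not support them.

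- *A 13-18% chance of wrongly concluding that video feedback works.* That figure counts errors in both directions. The chance of an error in the direction that would be read as benefit is about 6-9%. The inflation relative to a single test is similar, but the absolute figure is about half. Neither the correlation nor the success rule comes from the plan.
- *DOPS and satisfaction cannot be analysed as planned.* Their times are unstated, which is a gap. A group difference at one post-course assessment could still be written.
- *Three experiments mean three families of tests.* One sentence in Methods says three. Everything after it describes one comparison of two groups. The sentence needs clarifying, but it does not show separate testing.
- *The trial needs 64 per group whatever the analysis.* That number fits a two-sided post-test comparison. For change from pre-test, the same formula gives about 89, 64, 52 or 39 per group at r = 0.3, 0.5, 0.6 or 0.7.
- *The past tense of section 4 shows that results had been seen.* It does not settle this, so the fix has to cover both cases.

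**Conclusion.** The concern holds. Across the whole document no score, contrast or time point is made decisive, and one unadjusted 0.05 level covers everything. That absence is a matter of reading and rests on no assumption.

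The size is illustrative. It requires that any significant score be claimed, that no score has a true effect, and that the assumed correlations are about right. Even at correlation 0.9 the five-test rate is twice the nominal 5%, and in the direction favouring video feedback twice the nominal 2.5%. This should be fixed, because naming a primary test protects the error rate only if it is done before the group comparisons are known.

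The sample-size sentence is a separate error and adds no weight to the multiplicity point. It is wrong as written whichever score is chosen.

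**What to change.** **In section 4, before any group comparison is seen:**
1. Name one primary score, one GEE contrast and one time point, tested two-sided at 0.05. The choice is the sponsor's. Say what the t-test is for.
2. Make all other scores and times secondary. Either test them in a fixed sequence or with Holm, only after a significant primary result, or report estimates with 95% confidence intervals and no confirmatory claim.
3. State that the single comparison of 45 per group is the primary test, and reconcile the sentence about three experiments with that.
4. State the assessment times for DOPS and satisfaction.

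**If results have already been seen:** list every score-by-time test performed as the family, apply Holm across that whole list, and label the analysis as not pre-specified. Without a listed family, Holm leaves the same freedom of choice.

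**Separate correction to the sample-size sentence:** replace the 54. Keep the planned 45 per group and state its power as about 65% for a two-sided post-test comparison at d = 0.5. If a change or baseline-adjusted contrast is chosen, give the power for that contrast together with the assumed pre-post correlation.

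**Cost:** one paragraph and one restated sentence. Secondary scores lose unadjusted significance claims, and for a post-test comparison the plan would have to acknowledge power below 80%. No change in recruitment is needed.

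### The stated sample-size inputs give 128 students two-sided (102 one-sided), not 54, and the planned 45 per group is not tied to any power calculation

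*Combined protocol and SAP*

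**What the plan says.** The sample-size paragraph is at the end of section 4 (Statistical analysis). It gives the basis of the calculation as "Sample size was calculated using G*Power to compare differences between variables and independent means", then the inputs, "A power of 80% was used" with a "medium effect size (Cohen's d) of 0.5" and 5% alpha, and then the result: "This resulted in a sample size of 54 students", followed by a literature citation. It does not say whether the test is one- or two-sided, whether 54 is a total or a group size, or what dropout is allowed for.

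Section 1 (Participants) describes two groups, "each consisting of 45 individuals", which makes 90. No sentence connects 90 with 54.

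Two other statements bear on the point. The opening of the Methods says: "This study is divided into three randomized controlled experiments", although only one two-group comparison is then described. Section 4 assigns the intervention effect to another analysis: "Inferential statistics were performed using a generalized estimating equations to estimate the intervention effectiveness of the simulation course". No GEE model, working correlation or pre/post correlation is given.

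**The concern.** For two equal independent groups, d = 0.5 with 80% power at the 5% level is a standard case, and it needs well over 100 students two-sided. A result of 54 is less than half of that. The planned 90 matches neither figure.

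The 80% claim is the only reason the plan gives for its size. A reader of a null result would take it that a medium effect had been ruled out with 80% power. If true power on the sizing test is nearer 65%, an effect of d = 0.5 would be missed on that test about one time in three two-sided (1 − 0.65 = 0.35), or one in four one-sided (1 − 0.76 = 0.24).

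**Working it through.** **Inputs, all from section 4 unless noted.** Two independent means; d = 0.5; alpha 0.05; power 0.80; sidedness not stated, so both are shown. Equal groups of 45 come from section 1.

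**Formula.** With n per group, the two-sample t statistic has 2n − 2 degrees of freedom and noncentrality d × √(n/2). Power is the probability that this noncentral t exceeds the critical value (0.975 quantile two-sided, 0.95 quantile one-sided). The required n is the smallest whole number with power of at least 0.80.

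**Step 1: try to reproduce 54.**
- Two-sided: n = 63.77, so 64 per group, 128 in total (power 0.801).
- One-sided: n = 50.15, so 51 per group, 102 in total (power 0.806).
- The normal approximation gives nearly the same: 63 per group (126) and 50 per group (100).

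So 54 is not reproduced as a total. Nor is it reproduced as a group size, where the inputs give 64 or 51.

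**Step 2: power at the plan's numbers, d = 0.5.** For 45 per group, noncentrality = 0.5 × √(45/2) = 2.372 on 88 degrees of freedom; the critical values are 1.987 two-sided and 1.662 one-sided.

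| Reading | n per group | Two-sided | One-sided |
|---|---|---|---|
| 54 as a total | 27 | 0.438 | 0.567 |
| Planned enrolment | 45 | 0.650 | 0.761 |
| 54 per group | 54 | 0.731 | 0.826 |

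**Step 3: effect detectable with 80% power.** At 45 per group, d = 0.60 two-sided or 0.53 one-sided. At 27 per group, d = 0.78 or 0.69.

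**Step 4: can 54 be linked to 90?** Inflating for dropout as N/(1 − rate), 54/(1 − rate) = 90 needs a rate of 1 − 54/90 = 40%. No rate is stated.

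**Step 5: sensitivity (assumptions, not figures from the plan).**
- Dropout of 10% from 90 (40.5 per group): 0.604 two-sided, 0.721 one-sided. Dropout of 20% (36 per group): 0.553 and 0.676.
- If the 90 were split equally over three experiments (90/3/2 = 15 per group): 0.262 and 0.379. The plan does not say that this is so; the figures show only why the wording needs clarifying.
- Adjusting for the pre-test by ANCOVA at one time point, 45 per group, two-sided, with variance multiplied by 1 − r² and 87 degrees of freedom: power is 0.773 at r = 0.5 and 0.802 at r = 0.55, and reaches 0.80 at r = 0.547. A change-score analysis, with variance factor 2(1 − r), gives only 0.696 at r = 0.55, so the threshold of about 0.55 holds for ANCOVA alone.

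**The case against.** The strongest reply is that the t-test is not how the intervention effect will be estimated. Section 4 assigns that to GEE, and the OSCE and Mini-CEX are measured at three time points. Suppose an exchangeable correlation of 0.3 to 0.5 and d = 0.5 at both post-tests. Averaging the two and adjusting for the pre-test multiplies the variance by (1 + r)/2 − r², which is 0.56 at r = 0.3 and 0.50 at r = 0.5. Power at 45 per group is then about 88% to 91% two-sided. This stands as a limit on the conclusion: a loss of power in the GEE analysis is not shown. It does not rescue the sample-size statement, which names independent means and gives no correlation.

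Second, 54 may come from another calculation. Three routes reach it: a one-sided paired t-test at d = 0.5 needs 27, and 2 × 27 = 54; a repeated-measures interaction with f = 0.25, three time points and zero correlation gives 54 in total; and 51 per group one-sided with 5% dropout gives 51/0.95 = 53.7, so 54 per group. Each contradicts the stated method or needs an assumption the plan does not make. If one is the true source, the sentence misdescribes the calculation and still has to be corrected. The cited source cannot change what the stated inputs yield.

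Third, 54 per group one-sided does exceed 80%. That is correct, but it means 108 students and conflicts with 45 per group in section 1.

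Fourth, planned enrolment exceeds 54 by two thirds (90/54 = 1.67). It does, but it is still below both 102 and 128.

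**Conclusion.** The point holds. From its own inputs the plan needs 128 students two-sided or 102 one-sided. The stated 54, read as a total, has 44% or 57% power. The planned 90 is unconnected to the calculation and has 65% or 76%. The one reading of 54 that reaches 80% (per group, one-sided) contradicts the planned group size.

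This rests on equal groups, an unadjusted comparison at one time point, no dropout, and 45 per group applying to the comparison being powered. What is established is that the sole justification of size is wrong as written and that 90 falls short on the test used for sizing; nothing is established about GEE power. It must be corrected, because the 80% figure would otherwise be carried into the reading of the results.

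**What to change.** In section 4, delete 54 and the 80% statement attached to it, keep 45 per group as the single planned size, and write:

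> With 45 per group and two-sided alpha 0.05, an unadjusted two-group comparison at one time point has 65% power for d = 0.5 and 80% power for d = 0.60, before dropout.

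Also:
- Name the outcome and time point to which this refers.
- Confirm that 45 per group applies to that comparison, given the mention of three experiments. If the 90 are divided among experiments, recompute the power.
- If the sponsor prefers to base power on a pre-test-adjusted analysis at one time point, state the assumed pre/post correlation; about 0.55 or higher gives 80% for d = 0.5 at 45 per group with ANCOVA.
- If power is to be claimed for the GEE, state its model and the assumed correlations.

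The cost is protocol wording. Design, allocation and enrolment do not change. The only drawback is a less favourable stated power.
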